2 INTRODUCTION

This Statistical Analysis Plan (SAP) has been designed to document the planned analyses to be consistent with the objectives of the JETSTREAM China protocol. The specified analyses may be provided in reports to competent authorities and/or for scientific presentations and/or manuscripts. The primary analyses will be based on the single-arm procedure assessment (paired T-test) and 30-day post-procedure assessment for performance goal (PG).

Roll-in subjects will be analyzed separately for observational purpose.

3 PRIMARY ENDPOINTS ANALYSES

The sample size is justified by hypotheses parameters and driven by the 30-day primary safety endpoint to preserve adequate statistical testing power for either the primary effectiveness or the primary safety endpoints.

The primary effectiveness and safety hypotheses are planned for being tested after procedure and through 30 days, respectively at the pre-specified significance level of one-sided 2.5% each by the Bonferroni adjustment.

3.1 Primary Safety Endpoint

The 30-day MAE-free rate is selected to be assessed for the primary safety composite endpoint. The safety goal is designed to demonstrate that Jetstream meets the PG in terms of MAE-free rate through 30 days post-procedure.

3.1.1 Definition of MAE

Major Adverse Events (MAEs) defined as all causes of death, target limb unplanned major amputation, and/or target lesion revascularization (TLR) through 30 days

3.1.2 Safety Hypotheses

The primary safety hypothesis to be tested is that 30-day MAE-free rate in subjects treated with Jetstream meets the PG at a one-sided significance level of 2.5%.

The null hypothesis (H_0) states that the PG is not met as opposed to the alternative hypothesis (H_1) which states that the PG is met. The hypotheses inequalities are shown below:

$$H_0: Pt \leq PG \text{ (not met)}$$

$$H_1: Pt > PG \text{ (met)}$$

where Pt is the 30-day MAE-free rate for the subjects treated with Jetstream System and the PG is 88%. The PG of 88% is estimated on the basis of available literature and is consistent with those described atherectomy outcomes

3.1.3 Safety Sample Size

The overall sample size is consist of the primary cohort and roll-in subjects. The primary cohort is driven by the primary safety endpoint. Approximately 72 subjects are planned to be enrolled in the single-arm study. The sample size justification is based on the following assumptions.

- Power $\geq 90\%$
- One-sided significance level (alpha) = 2.5%
- PG for 30-day MAE-free rate = 88%
- Expected 30-day MAE-free rate = 99%
- Attrition rate in 30 days = 15%
- N = 50 evaluable subjects are required at 30 days
- A maximum of N = 60 subjects to be enrolled in the primary cohort at baseline
- With additional 2 roll-in subjects per site, the overall subjects to be enrolled are approximately 72.

3.1.4 Safety Statistical Methods

A normal approximation test for comparing observed 30-day MAE-free rate with the PG will be used to assess the safety hypotheses for a minimum of 50 evaluable subjects.

3.1.5 Worst Case Assessment for Safety

The PG of 88% will only allow 1 subjects with 30-day MAE out of 50 subjects treated with Jetstream. That is, the observed 30-day MAE-free rate in Jetstream will need to be at least 98% (49/50) in order to claim safety PG.

3.1.6 Additional Justification of Sample Size Parameters

The PG of 30-day MAE-free rate for Jetstream was based on the DEFINITIVE Ca++ study results (Roberts et. al. 2014), published by Catheterization and Cardiovascular Interventions. The 95% lower confidence limit 88.3% was reported.

The 30-day freedom from MAE rate was 93.1% (122/131) in DEFINITIVE Ca++ study with 95% exact confidence intervals: 87.4%, 96.8% estimated by SAS.

3.2 Primary Effectiveness Endpoint

The acute reduction of percent diameter stenosis (%DS) within a subject post atherectomy but prior to any adjunctive therapy is chosen to be assessed for the primary effectiveness endpoint. The goal is set to demonstrate that within a subject, the %DS in post treatment is smaller than the %DS in before-treatment by a pre-specified reduction during the procedure.

3.2.1 Definition of Acute Reduction

The acute reduction of %DS is defined to compare the post atherectomy but prior to any adjunctive therapy to its baseline diameter stenosis.

3.2.2 Effectiveness Hypotheses

The primary effectiveness hypothesis to be tested is that the acute reduction of %DS in subjects treated with Jetstream System exceeds 40%* within subject at a one-sided significance level of 2.5%.

The null hypothesis (H_0) states that there is no treatment effect before and after subjects treated with Jetstream System as opposed to the alternative hypothesis (H_1) which states that there is a treatment effect. The hypotheses inequalities are shown below:

$$H_0: \Delta t \leq 0 \text{ (not met)}$$

$$H_1: \Delta t > 0 \text{ (met)}$$

where Δt is the averaged difference in acute reduction of %DS before and after the subjects treated with Jetstream System and the within-subject treatment effect is 40% with standard deviation of 18% derived by the Pathway PVD study, Jetstream Calcium study and JET Registry.

*The expected mean acute reduction (i.e. %DSbefore Jetstream – %DSafter Jetstream) was 40%; the primary effectiveness hypothesis is to demonstrate there is a significant acute reduction (>0).

3.2.3 Effectiveness Sample Size and Power Analysis

The power analysis for the primary effectiveness endpoint is based on the following assumptions.

- One-sided significance level (alpha) = 2.5%
- Expected acute reduction of %DS = 40% with the standard deviation = 18%, within the range of historical data

The sample size is driven by the primary safety endpoint to provide at least 99% power to assess the primary effectiveness endpoint.

3.2.4 Effectiveness Statistical Methods

A paired t-test for the reduction in %DS before and after subjects treated with Jetstream System will be used to assess the effectiveness hypotheses for a minimum of 50 evaluable subjects.

3.2.5 Worst Case Assessment for Effectiveness

The mean and standard deviation of the reductions are based on each subject's change in %DS before and after atherectomy. If the standard deviation of 18% is observed, the acute reduction of %DS will be at least 6% to claim a success. Other scenarios are shown below.

Standard Deviation in Reduction (%DS)	Minimal Diff in Reduction (%DS)
8-10	3
11-14	4
15-17	5
18-21	6
22-24	7
25-28	8
29-31	9
32-35	10

3.2.6 Additional Justification of Sample Size Parameters

The expected acute reduction of %DS was based on the Pathway PVD study, Jetstream Calcium study, and JET Registry.

The before-and-after atherectomy in the Pathway PVD shows $79.4\% \pm 17.7\%$ and $35.0\% \pm 16.1\%$ respectively. The before-and-after atherectomy in Jetstream Calcium study shows $86.9\% \pm 9.0\%$ and $37.0\% \pm 13.0\%$. The before-and-after atherectomy in JET Registry shows $91.1\% \pm 9.8\%$ and $44.4\% \pm 20\%$, and the acute reduction of %DS is $46.7\% \pm 20.5\%$.

3.3 Success Criteria

The success criteria are defined hierarchically. The primary effectiveness hypothesis will be performed at only when the primary safety hypothesis is achieved.

3.3.1 Success Criteria for the Primary Safety Endpoint

Jetstream System will be concluded as meeting PG for device safety if the one-sided lower 97.5% confidence bound on the observed 30-day MAE-free rate is greater than 88%.

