#### 11.1.1.2. Safety Sample Size

The overall sample size is consist of the primary cohort and roll-in subjects. The primary cohort is driven by the primary safety endpoint.

- Power  $\geq 90\%$
- One-sided overall significance level = 2.5% (alpha)
- PG for 30-day MAE-free rate = 88%
- Expected 30-day MAE-free rate = 99%
- Attrition rate = 15% (loss to follow-up at 30 days)
- A minimum of 50 subjects to be evaluable at 30 days that will provide at least 99% power for the primary safety endpoint
- A sample size of 60 subjects to be enrolled in the primary cohort at baseline

With additional 2 roll-in subjects per site, the overall subjects to be enrolled are approximately 80.

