#### 11.1.1.3. Safety Statistical Test Method

A normal approximation test (e.g. Chi-Square Test) will be used to assess the one-sided hypothesis of PG.

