### 11.2. *Success Criteria*

#### Success Criteria for Primary Safety Endpoint

Jetstream System will be concluded as meeting PG for device safety if the one-sided lower 97.5% confidence bound on the observed 30-day MAE-free rate is greater than 88%.

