7.3 SAS Codes for Chi-Square Test

The confidence intervals and the p-value for the chi-square test can be produced by the following SAS code.

```
proc freq data=;
  tables xx/binomial(p=) alpha=;
  run;
```

For example, the worst case scenario in the PG testing of the primary safety hypotheses is used for the exercise. A dummy frequency table is coded as below.

```
%let total=50; %let yes=49; %let no=&total.-&yes.;

data dsn1;
  yn=1; wgt=&yes.; output;
  yn=0; wgt=&no.; output;
run;
```

A list of SAS codes for Binomial and Chi-Square method is used for PG=88% and 95% confidence limits.

```
proc freq data=dsn1 order=data;
  tables yn/ binomial(p=0.88) alpha=.05;
  weight wgt;
run;
```

The SAS output for the worst case scenario is presented below.

Binomial Proportion	
yn = 1	
Proportion	0.9800
ASE	0.0198
95% Lower Conf Limit	0.9412
95% Upper Conf Limit	1.0000
Exact Conf Limits	
95% Lower Conf Limit	0.8935
95% Upper Conf Limit	0.9995
Test of H0: Proportion = 0.88	
ASE under H0	0.0460
Z	2.1760
One-sided Pr > Z	0.0148
Two-sided Pr > Z	0.0296
Sample Size = 50	

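### The primary safety success rule names no confidence-bound method, and the two limits the SAP prints give opposite verdicts at 2 MAEs in 50

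*SAP*

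**What the plan says.** SAP 3.3.1 declares the safety performance goal met if "the one-sided lower 97.5% confidence bound on the observed 30-day MAE-free rate is greater than 88" percent. Protocol 11.2 and both synopses carry the same criterion. None of them names an interval method.

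What is named is a test. Protocol 11.1.1.3: "A normal approximation test (e.g. Chi-Square Test) will be used to assess the one-sided hypothesis of PG". SAP 3.1.4: "A normal approximation test for comparing observed 30-day MAE-free rate with the PG will be used to assess the safety hypotheses".

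SAP 7.3 supplies PROC FREQ code for both the intervals and the p-value: "A list of SAS codes for Binomial and Chi-Square method is used for PG=88% and 95% confidence limits". Its output for 49/50 shows an asymptotic lower limit of 0.9412, an exact lower limit of 0.8935, and Z = 2.1760 (standard error under the null) with one-sided p = 0.0148. It does not say which limit decides.

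SAP 3.1.5 gives the consequence at one sample size: "The PG of 88% will only allow 1 subjects with 30-day MAE out of 50 subjects treated with Jetstream".

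On sample size, SAP 3.1.3 has "A maximum of N = 60 subjects to be enrolled in the primary cohort at baseline" with 15% attrition, and Protocol 11.1.1.2 has "A minimum of 50 subjects to be evaluable at 30 days that will provide at least 99% power for the primary safety endpoint".

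**The concern.** This is the pass/fail line for the primary safety claim of a single-arm study, and it is written as a bound. The usual bound that goes with a normal approximation is the Wald limit, which is also the first one in the SAP's output. Wald limits are too high when the proportion is near 1 and n is small, which is the situation here. If the Wald limit decides, an outcome that SAP 3.1.5 calls a failure becomes a success, and the 2.5% one-sided error rate is not held. If the limit is chosen only after the MAE count is known, the decision depends on the data. The only worked example, 49/50, passes under both limits, so it does not reveal the conflict.

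**Working it through.** **Inputs.** Performance goal 0.88, one-sided alpha 0.025, expected rate 0.99, 50 evaluable, 60 enrolled in the primary cohort, 15% attrition (SAP 3.1.3). Attrition from 60 leaves 60 × 0.85 = 51. The alternative rate of 93.1% (122/131) comes from SAP 3.1.6.

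**Formulas.** With x MAE-free subjects of n and p = x/n:
- Wald limit: p − 1.96·√(p(1−p)/n)
- Exact limit: the 2.5% quantile of Beta(x, n−x+1)
- Z test: (p − 0.88)/√(0.88·0.12/n)
- Type I error: P(X ≤ c), with X the MAE count from Binomial(n, 0.12) and c the largest count the rule allows
- Power: the same probability under Binomial(n, 0.01)

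**Reproducing the SAP at 49/50.** Wald: 0.98 − 1.96·√(0.98·0.02/50) = 0.9412. Exact: 0.8935. Z = 0.10/√(0.1056/50) = 2.176, p = 0.0148. All match SAP 7.3, and every method declares success.

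**One more MAE, 48/50.** Wald: 0.96 − 1.96·√(0.96·0.04/50) = 0.9057, success. Exact: 0.8629, failure. Z = 0.08/√(0.1056/50) = 1.741, p = 0.0409, failure. SAP 3.1.5: failure. At 47/50 the Wald limit is 0.8742, so the Wald rule allows exactly 2 MAEs at n = 50.

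**Across evaluable n.**

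| n | MAEs allowed: Wald / exact / Z | Type I error: Wald / exact |
|---|---|---|
| 50 | 2 / 1 / 1 | 5.1% / 1.3% |
| 51 | 2 / 1 / 1 | 4.7% / 1.2% |
| 53 | 3 / 1 / 1 | 10.7% / 0.9% |
| 60 | 3 / 2 / 2 | 6.0% / 2.0% |

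Over n = 45 to 60, Wald allows 2 MAEs up to n = 52 and 3 from n = 53. Exact allows 1 up to n = 57 and 2 from n = 58. The Z test allows 1 up to n = 56 and 2 from n = 57. The Wald error is lowest at n = 52 (4.2%), so it exceeds 2.5% throughout. At n = 60 with 3 MAEs, Wald gives 0.8949 (success), while exact gives 0.8608 and Z = 1.669 (both failure).

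**Z test against exact bound.** They part at n = 57 with 2 MAEs. Z = 1.973 passes, the exact limit of 0.8789 fails, and the Z rule's true error is P(X ≤ 2 | 57, 0.12) = 2.63%.

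**How often the choice of limit matters.** At n = 50, Wald and exact differ only at exactly 2 MAEs. That has probability 7.6% if the true MAE-free rate is 99%, and 18.9% if it is 93.1%. At 99% the disagreement probability is 7.8% at n = 51, 10.9% at n = 57 (2 or 3 MAEs) and 1.9% at n = 60.

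**Power at n = 50, true rate 99%.** Exact or Z rule: P(X ≤ 1) = 0.6050 + 0.3056 = 0.9106. Wald rule: 0.9106 + 0.0756 = 0.9862. A normal approximation gives 0.922 with the null variance and more than 0.999 with the alternative variance. Only the last reaches the stated 99%.

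**The case against.** The strongest reply is that the decision is already fixed in substance. Both documents name a normal-approximation test of the 88% goal, SAP 7.3 runs it with the null standard error, and SAP 3.1.5 allows 1 MAE in 50. At n = 50 these agree with each other and with the exact limit. Nothing says the Wald limit decides, since it is default software output. On this view the 5.1% belongs to a reading the SAP excludes, and it would be enough to name the Wilson bound, which inverts the Z test.

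Part of this stands. At n = 50 the Wald reading does contradict SAP 3.1.5, and the Wilson bound would be consistent with that section. But 3.1.5 settles a single sample size. Fifty is a minimum, the plan's own attrition gives 51, and up to 60 may be evaluable. The binding criterion is a bound, and the named test does not specify one. The Z test, and so the Wilson bound, also exceeds 2.5% at n = 57, though only by 0.13 points.

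A second reply is that the exact rule costs power: at a true rate of 99% it has 89.8%, 89.5%, 89.2% and 88.9% at n = 54 to 57, below the planned 90%. The figures are right. At n = 54 to 56, however, the Z test also allows only 1 MAE and has the same power. The cost peculiar to the exact rule is at n = 57, where the Z test has 98.0%.

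**Conclusion.** The concern holds and should be corrected before the primary analysis. The success rule is incomplete, and at reachable outcomes the verdict depends on which printed limit is read. The Wald reading has a true error of 4.2% to 10.7% for 50 to 60 evaluable subjects, against 2.5%; the exact reading never exceeds 2.5%. The safety power at n = 50 is about 91% under the SAP's own 1-in-50 limit, not 99% or more, although the design input of at least 90% is still met there.

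These figures assume independent binomial outcomes, a true rate of 88% for type I error, and 99% for power. The Wald error rates describe one permissible reading; the plan does not expressly adopt it.

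A related wording slip does not carry the finding. SAP 3 describes 2.5% for each endpoint as a Bonferroni adjustment. It is not one, and none is needed, because Protocol 11.2 and SAP 3.3.3 require both endpoints to be met.

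**What to change.** - In Protocol 11.2, SAP 3.3.1 and both synopses, name the exact (Clopper-Pearson) one-sided 97.5% lower bound as the sole decision rule.
- In Protocol 11.1.1.3, SAP 3.1.4 and the synopsis entries for the test, replace the normal-approximation test with the matching exact binomial test, or label it supportive.
- In SAP 7.3, state that the asymptotic limit is not used for the decision.
- In SAP 3.1.5, give the allowed count by evaluable n: 1 MAE for n = 45 to 57, 2 for n = 58 to 60. Extend the table if more than 60 could be evaluable. SAP 3.1.3 treats 60 as a maximum, Protocol 9.3 as a minimum, and SAP 5.2 speaks of 72 subjects in the primary endpoint report.
- Restate the safety power as about 91% at n = 50, and disclose that it falls slightly below 90% at n = 54 to 57.
- In SAP 3, delete the Bonferroni reference and say that both endpoints must be met, each at one-sided 2.5%.

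The cost is a few lines of text, with no change to sample size or data collection; SAP 5.16 provides for such an amendment before the primary analysis. The 1-in-50 limit is kept. The counts at other n are new to the SAP but follow by calculation.

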3.3.2 Success Criteria for the effectiveness Endpoint

Jetstream System will be concluded as meeting endpoint for device effectiveness if the one-sided lower 97.5% confidence bound on the difference between before and after atherectomy in %DS within subject is greater than zero.

3.3.3 Success Criteria for the Study

If the primary safety and the primary effectiveness endpoints are both met, the study will be considered a success and both device safety and effectiveness will be claimed. The success criteria is defined hierarchically. The primary effectiveness hypothesis will be performed at only when the primary safety hypothesis is achieved.

4 GENERAL STATISTICAL CONSIDERATION

4.1 Analysis Sets

The primary and pre-specified additional endpoints will be analyzed on an ITT basis and on a per-protocol basis. For the ITT analysis, all subjects who sign the written ICF and are enrolled in the study will be included in the analysis sample, regardless of whether the subject used the Jetstream System. For the per-protocol analysis, only enrolled subjects who are treated with the study device in the target lesion will be included in the analysis sample.

Data from per-protocol cohort and Roll-in cohort will be analyzed separately for observational purpose.

4.2 Control of Systematic Error/Bias

Selection of subjects will be made from the investigators' general or professional referral population. All subjects meeting the inclusion/exclusion criteria that have signed the protocol-specific ICF will be eligible for enrollment in the trial. Consecutively eligible subjects should be enrolled into the study to minimize selection bias. In determining subject eligibility for the study, the investigator's assessment of imaging will be used. The effectiveness endpoint data obtained from the core laboratory and the safety adjudicated data from independent Clinical Event Committee (CEC) will be used for the primary analyses.

4.3 Enrollment for Each Investigative Site

The enrollment cap for each study site is 35% of total enrolled subjects. No study sites will be allowed to enroll more than 35% (N=25) of the total number of enrolled subjects to avoid treatment center bias and ensure homogeneous study results.

4.4 Baseline Data Analyses

Subject demographics, and clinical characteristics, site-reported and core lab reported lesion characteristics, procedure assessment, device information, and medication compliance will be summarized using descriptive statistics. The analysis level may be (but will not be limited to) by subject, lesion, procedure, or device.

For continuous and/or ordinal variables, the descriptive statistics will include mean, standard deviation, number evaluated, minimum and maximum. Some specific variables may also include additional statistics such as median and confidence intervals. For binary or categorical variables, the descriptive statistics will include percentage, numerator, denominator, and number evaluated. Some variables may include confidence intervals as needed.

At baseline demographics, medical history, cardiac history, Neurological history, peripheral vascular history and lesion characteristics like lesion type, lesion classification, Target lesion final outcome will be reported.

At procedure, procedure characteristics and study device used by Catheter model and tip diameter will be reported.

5 ADDITIONAL STATISTICAL ANALYSES

5.1 Secondary Endpoints Assessments

Secondary assessments may refer to (but not limited to) peri-procedural complications, clinical/procedural/hemodynamic success, safety/effectiveness endpoints, any type of AE rates at time points that data is collected (refer to the protocol section 7.2). All additional assessments are observational

- Procedural success, defined as $\leq 30\%$ residual angiographic stenosis in 2 near-orthogonal projections by visual assessment, after successfully debulking the target lesion and adjunctive interventions (such as percutaneous transluminal angioplasty/stenting) without any MAE within 24 hours post index procedure
- Primary (vessel) patency of the treated segment assessed by duplex ultrasound sonography (DUS) at 6 and 12 months post-procedure without TLR
- Clinical success rate (defined as improved Rutherford classification by at least +1 class compared to baseline) at 30 days, 6 and 12 months
- Hemodynamic success rate (defined as positive change in Ankle-Brachial Index) at 30 days, 6 and 12 months
- MAE rate 6 and 12 months post-index procedure
- All-cause death at 30 days, 6 and 12 months
- Clinically-driven TLR and TVR rate at 30 days, 6 and 12 months
- Target limb major amputation at 30 days, 6 and 12 months
- Rate of peri-procedural complications:
 - Perforation at treated segment
 - Abrupt closure at treated segment (including dissection and thrombosis)
 - Significant dissection (types C – F) at treated segment
 - Aneurysm at treated segment
 - Distal embolization

Note that the vessel patency is defined as freedom from more than 50% stenosis based on DUS peak systolic velocity ratio (PSVR) comparing data within the treated segment to the proximal normal arterial segment. A systolic velocity ratio > 2.4 suggests $> 50\%$ stenosis.

No formal tests of hypotheses are proposed for secondary endpoints. Statistical comparisons may be performed for exploratory purposes. No formal inferences are planned on the additional assessments and therefore alpha-adjustments for multiple comparisons will not be used.

All additional assessments are observational.

For Primary endpoint report (30-Day) below Secondary Assessments will be performed:

- Procedural success.
- Clinical success rate at 30 Days.
- Hemodynamic success rate at 30 Days.
- All-cause death at 30 days.
- Clinically-driven TLR and TVR rate at 30 days.
- Clinically-driven TLR and TVR rate at 30 days.
- Target limb major amputation at 30 days.
- Rate of peri-procedural complications.

For 12-Month report below Secondary Assessments will be performed:

- Procedural success.
- Primary (vessel) patency of the treated segment assessed by duplex ultrasound sonography (DUS) at 6 and 12 months post-procedure without TLR
- Clinical success rate at 30 days, 6 and 12 months.
- Hemodynamic success rate at 30 days, 6 and 12 months.
- MAE rate 6 and 12 months post-index procedure.
- All-cause death at 30 days, 6 and 12 months.
- Clinically-driven TLR and TVR rate at 30 days, 6 and 12 months.
- Target limb major amputation at 30 days, 6 and 12 months.
- Rate of peri-procedural complications.

